1 ABBREVIATIONS USED IN THE PROTOCOL

Abbreviation Term

IANB Inferior Alveolar Nerve Block

GMC Geisinger Medical Center
IRB Institutional Review Board

ASA American Society of Anesthesiologists
AAPD American Academy of Pediatric Dentistry

MRN Medical Record Number

PA Pennsylvania

FLACC Faces, Legs, Arms, Crying Consolability

[figure not shown]
2 ABSTRACT

Local anesthetic buffered with sodium bicarbonate has been suggested to reduce pain, discomfort and onset time of local anesthesia on injection into tissue, compared to non-buffered solutions. Buffered local anesthesia has been used in medicine, however intraoral injections with buffered solutions are less common in dentistry. Most research has focused on adult perception of pain on administration of buffered local anesthetic. There have been few studies and inconclusive evidence to show that buffered lidocaine reduces the perception of pain on administration in children. The purpose of this interventional study is to assess pain reduction and onset time on injection of buffered 2% lidocaine with 1:100,000 epinephrine in children.

3 BACKGROUND AND SIGNIFICANCE

Local anesthesia is a necessary component of dental treatment that aids in establishing patient comfort and reduction of anxiety. However, a local anesthesia injection is often uncomfortable and unpleasant. Injection of local anesthesia can elicit a painful or burning sensation. In children, profound anesthesia and ease of administration can help establish and maintain positive dental experiences and also reduce anxiety in the dental setting. The injection is not only uncomfortable during the penetration of the needle through the epidermis, but also during injection of acidic solution into the tissue.

Commercially available local anesthetics are often prepared with hydrochloric acid to increase their solubility and stability¹. These local anesthetics range in pH from 3.5 to 5.5 and are significantly lower than the physiological pH of 7.35. The acidity of a traditionally prepared local anesthetic solution has been shown to contribute to pain during injection of local anesthetic and also to an increased onset time of local anesthesia². Buffering the traditional local anesthetic solution to a pH value closer to physiological pH has been done to aid in pain reduction associated with injection of solution². Based on the Hederson-Hasselbach equation, it has been

shown that neutralizing the solution of local anesthesia can reduce the pain perception associated with administration of local anesthesia and decrease the onset time³. With an increase in pH of solution, more free base is available to cross the nerve sheath, reducing the onset of action³.

Medicine has used buffered local anesthetic solutions with success and the literature reflects this adaptation into clinical practice.^{3,4,5,6} Previous studies have investigated the difference in onset and the reduction of pain in administration of buffered lidocaine vs traditional lidocaine in both children and adults. There have been fewer studies investigating the perception of discomfort during injection and the difference in anesthesia onset time in children compared to adult subjects. The literature has shown varied results and conclusions in both children and adult study populations. Some of these studies have found a significant difference in onset time and perceived pain reduction with buffered solution compared to standard solution, while others have failed to find significant differences.^{1,7,8,9,10,11}

[figure not shown]
This project's primary aim is to evaluate pain perception in buffered vs non-buffered local anesthetic administration in children undergoing routine dental treatment. The secondary aim is to evaluate if the buffered solution results in a faster onset of local anesthesia compared to conventional solution. Through a well-designed study, we hope to contribute to the profession's understanding of advanced local anesthesia techniques in children.

4. HYPOTHESIS AND SPECIFIC AIMS

4.1 HYPOTHESIS:

- 4.1.1 Null Hypothesis: There will be no significant difference between buffered local anesthesia vs conventional anesthesia in pain reduction.
- 4.1.2 Null Hypothesis: There will be no significant reduction in time between buffered local anesthesia vs conventional anesthesia achieving soft tissue anesthesia.
- 4.1.3 Hypothesis: There will be a statistically significant reduction in pain on intraoral administration of buffered 2% lidocaine with 1:100,000 epinephrine compared to non-buffered 2% lidocaine w/1:100,000 epinephrine in children.
- 4.1.4 Hypothesis: Buffered 2% lidocaine with 1:100,000 epinephrine will have a statically significant faster onset of soft tissue anesthesia compared to non-buffered 2% lidocaine w/1:100,000 epinephrine in children

4.2 SPECIFIC AIM 1:

To determine if buffering 2% lidocaine with 1:100,000 epinephrine reduces discomfort experienced on injection compared to non-buffered solution in children with a split mouth design

4.3 SPECIFIC AIM 2:

To compare infiltration vs inferior alveolar nerve block (IANB) in experience of pain reduction with buffered 2% lidocaine with 1:100,000 epinephrine on injection in children among different groups; patients will either receive two or more infiltrations or two or more IANBs.

4.4 SPECIFIC AIM 3:

To determine if buffering 2% lidocaine with 1:100,000 epinephrine reduces onset time of local anesthesia compared to non-buffered solution in children

4.5 SPECIFIC AIM 4:

[figure not shown]
To compare onset time of local anesthetic via infiltration versus IANB using buffered 2% lidocaine with 1:100,000 epinephrine in children

5. STUDY DESIGN

5.1 DESCRIPTION

This study has been designed as a longitudinal, double blind, crossover study. Specifically, a split mouth design will be implemented to investigate if there is a significant difference in pain perception between administering buffered local anesthesia versus conventional local anesthesia in a pediatric patient. We will also investigate time of onset of local anesthesia and compare buffered to non-buffered solutions. Patients will be treated by a single pediatric dental resident while being overseen by a board-certified attending pediatric dentist at Geisinger Medical Center (GMC). This study will be implemented upon receiving Institutional Review Board (IRB) approval.

The population of interest includes healthy children aged 4-17yo. Children selected for this study will be assessed using the American Society of Anesthesiologists (ASA) physical status classification system. In an effort to control for confounding variables, only healthy children classified as ASA I or ASA II will be included in this study. Children selected for this study will have been determined to require treatment on two or more occasions on opposite sides of the mouth. If a patient has multiple issues on each side of the mouth, the patient may be asked to participate in the study procedures for a second time. This could result in seeing the patient for 4 separate visits. Patients will not be excluded if they develop localized infection requiring treatment without systemic antibiotics, however, they will only remain in the study if both sides requiring treatment are either free of infection or if both sides have a localized pain or infection requiring treatment without systemic antibiotics. Patients must have no allergy to lidocaine or

history of adverse reactions to epinephrine, no history of hyperthyroidism, and no significant cardiovascular disease per recommendations for administration of local anesthetic according to the American Academy of Pediatric Dentistry (AAPD).¹² Buffered lidocaine has been approved for use in patients for medical and dental procedures. There is no additional cost to the patient for receiving buffered versus non-buffered solution.

Patients will be examined by the pediatric dental resident under supervision of the attending pediatric dentist. At the time of examination, patients that meet the inclusion criteria (see section 5.2.2 below) will be offered to enroll in this research study. Each patient will consent for treatment via a parent or legal guardian. The parent or legal guardian and the provider will review the inclusion and exclusion criteria, risks and benefits to participation in this study, and general information about the timeline and clinical expectations of the patient. The consent process will be completed by the pediatric dental resident under supervision of the attending pediatric dentist. The patient's parent or legal guardian will be given a chance to ask questions during the consent process. Parents and legal guardians will be given the option to have their child included in the study or to have their child proceed with traditional treatment with non-buffered local anesthesia. Study participants are those that will be consented to receive a blinded solution of either buffered or non-buffered solution over two or more appointments. There will be no financial compensation or incentive to participate in this study. There is no advantage or disadvantage for patients undergoing treatment in this study as compared to patients not included in the study. Compared to patient's not included in the study, there is no additional risk with patients electing to be removed from the study or for patients who fail to complete treatment. In addition to obtaining parental or guardian consent, patients aged 15-17 years of age will sign assent. Study participants will receive a copy of this consent/assent form.

Following patient selection (based on the inclusion and exclusion criteria listed below in section 5.2.2), and consent, each patient will be assigned number as they are added into the study. This number will be sequential; e.g. the first patient will be assigned a number of '1,' and the second patient will be assigned a number of '2.' Patients will be added to the study at time of consent after the initial examination by the dental resident.

On the day of the procedure, the side of the mouth that is treated first will be based on the patient's chief complaint. If the patient does not have a chief complaint, the side of the mouth that is treated first will be the side of the mouth with more significant dental caries. The attending pediatric dentist will flip a coin to determine if the patient will receive the buffered or conventional local anesthetic solution during the first visit, with the "heads" side being assigned to the buffered solution, and the "tails" side assigned to the non-buffered solution. At the patient's second visit, the alternative local anesthetic solution will be used, and the other side of the mouth will be treated.

IRB NUMBER: 2019-0408 IRB Approved: 12/12/2019

[figure not shown]
The attending pediatric dentist will have access to a protected Excel spreadsheet containing information related to each patient including: patient name, medical record number (MRN), the patient's number assignment (as discussed above), date of the first and second visit, which local anesthetic solution was administered at each visit, the local anesthesia technique used (infiltration vs IANB), which arch (maxilla vs mandible) was treated, and which side of the mouth was treated. This document will be locked and the operator will not have access to this spreadsheet in order to preserve the double-blind nature of this study.

Vasoconstrictors, like epinephrine, become unstable with an increase in pH⁹. Local anesthetic solutions with a vasoconstrictor are traditionally prepared as an acidic solution to extend shelf life⁹. Buffering our local anesthesia containing epinephrine will reduce the stability of solution from approximately 8-12 months to a shelf life of only seven days¹³. Although the solution has been said to be stable for a week, to ensure stability of the solution, and control for confounding variables, the buffered solutions will be mixed immediately before administering the solution. Other study designs have used this approach to mix the solution immediately before administration^{1,9}.

During the appointment requiring the buffered local anesthesia solution, the attending will prepare 1:10 dilution of sodium bicarbonate to local anesthesia. A 1.7mL vial of commercially available 2% lidocaine hydrochloric acid with 1:100,000 epinephrine (Lignospan standard, Septodont Lancaster, Pennsylvania (PA) will be used. The cartridge of lidocaine and the bottle of sodium bicarbonate will be wiped with an alcohol pad. 0.17mL of 8.4 percent sodium bicarbonate will be added into the local anesthesia cartridge to make the final preparation. The pH of traditional 2% lidocaine with 1:100,000 epinephrine is typically acidic to prolong shelf life; the pH is approximately 4.5.8 The buffered solution will be tested using a pH tester (Water Quality Test Meter Pancellent TDS PH EC Temperature 4 in 1 Kit, Pancellent) to evaluate the pH range of this preparation, and to verify a value above 5.5.

The attending will bring the cartridge of anesthetic to the operatory and load the syringe. The operator and patient will remain blinded to the type of local anesthesia that is used. For this study, if the patient requires treatment of the lower posterior teeth, a IANB will be the injection technique of choice. If the patient requires treatment in the posterior maxilla, an infiltration will be the injection technique of choice. After a period of no less than one week, the patient will return for a second visit. At the second visit, the solution of local anesthesia will be alternated, and the opposite side of the mouth will be treated.

Prior to initiation of treatment, patients will rate their pain using the Wong-Baker FACES Pain Scale in order to establish a baseline and to help eliminate confounding variables. Also before treatment, a tooth that will be anesthetized will be probed with a periodontal probe to establish a baseline perception of this sensation without local anesthesia. Upon probing without local anesthesia, the patient will ask if they feel a "pinch," in order to

establish this baseline. When asked if they feel a pinch, patients will respond with a "yes" or "no" answer, which will be recorded.

Topical 20% benzocaine (Ultracare Oral Anesthetic Gel, Ultradent, South Jordan, Utah will be used on the intraoral tissue at site of injection for 5 minutes, and then the tissue will be injected. Patients will be informed when the tissue is pierced and again when the local anesthesia is being administered. Participants receiving an IANB will be injected with 0.85mL (50% volume of a 1.7mL carpule) of 2% lidocaine with 1:100,000 epinephrine approximately. Patients receiving a buccal infiltration in the maxilla will receive 0.425mL (25% volume of a 1.7mL carpule) of solution over 15 seconds. The operator will aspirate prior to administration of local anesthetic solution in all cases; a positive aspiration will require redirection of the needle or repositioning before injection. Patients will be asked to rate their pain related to administration of solution (the second prompt) once the injection is finished. Patients will be observed during injection and assessed by the operator using the Faces, Legs, Arms, Crying Consolability (FLACC) scale. Immediately after local anesthesia, patients will be asked to rate the pain of injection of solution using the Wong-Baker FACES Pain Scale. These scales were selected because they are approved for use by the AAPD for children over the age of 3 and have been used successfully in previous studies investigating pain perception in child subjects.^{7,14}

After administration of local anesthetic solution, the onset time of soft tissue anesthesia will be measured by using a periodontal probe in the sulcus of the anesthetized tooth or a single tooth in the anesthetized quadrant. This probing will be initiated 15 seconds after initial injection of anesthetic solution and will be repeated at 15 second intervals until local anesthesia is achieved. After each probing attempt, patients will be asked if they felt a "pinch". Once the patient answers "no," the time of onset, in number of seconds to achieve anesthesia from injection to a "no" answer, will be recorded.

In the event of a missed block, the patient will be excluded from the study. The second attempt for local anesthesia will be made with the effort to achieve profound local anesthesia, and the technique and type of local anesthesia will not be limited to the techniques or anesthetic solutions described in this study. Local anesthesia techniques and solutions used in the event of a missed block will be within the scope of practice for a pediatric dental patient, however, this event will be considered a potential confounding variable in our research study.

A second protected Excel spreadsheet will be used to record patient's scores for the Wong-Baker FACES Pain Scale, the FLACC scale and the time of onset of local anesthesia. This spreadsheet will also include the patient's name, MRN number, the side of the mouth that was treated, the location of the injection, the injection technique, and the date of each visit. This spreadsheet will be available to the operator in order to record the clinical outcomes related to each encounter; it will not affect the double-blind nature

GEISINGE IRB NUMBER: 2019-0408 IRB Approved: 12/12/2019

of this study, as the operator will not know which local anesthetic preparation was used during each encounter.

After the first day of treatment, a "wash out" period of at least 1 week will be required before the patient can return for treatment on the other side of the mouth, and the administration of the alternate type of local anesthetic solution. Wash out periods have been used in many similar studies to minimize bias.^{1,7,11}

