5.3 RECRUITMENT

Study participants will be screened by a treating dentist from a GMC dental clinic at time of comprehensive oral exam or periodic oral exam. Patients may be added to the study by the treating dentist based on the inclusion criteria. Study participants will be recruited from the outpatient Foss clinic of Geisinger Medical Center in Danville, PA and from the outpatient Milton clinic of Geisinger Medical Center in Milton, PA.

IRB NUMBER: 2019-0408 IRB Approved: 12/12/2019

Recruitment of study participants will be done by the treating pediatric dental resident or attending pediatric dentist at the time of exam. Patients will be recruited from the outpatient Foss clinic in Danville, PA and the outpatient Milton clinic in Milton, PA at Geisinger Medical Center.

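### Solution order rests on one unrecorded coin flip by the unblinded attending; a pre-generated, concealed and logged order list would make the allocation verifiable at almost no cost

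*Combined protocol and SAP*

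**What the plan says.** Section 5.1 makes the allocation in one step: "The attending pediatric dentist will flip a coin to determine if the patient will receive the buffered or conventional local anesthetic solution". Heads means buffered at the first visit and tails means non-buffered. The second visit follows automatically: "At the patient's second visit, the alternative local anesthetic solution will be used, and the other side of the mouth will be treated". One flip therefore fixes both visits and both sides.

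Which side goes first is not random. "On the day of the procedure, the side of the mouth that is treated first will be based on the patient's chief complaint"; without a chief complaint, "the side of the mouth that is treated first will be the side of the mouth with more significant dental caries".

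The person who flips is close to the child and to the drug. At enrolment, "Patients will be examined by the pediatric dental resident under supervision of the attending pediatric dentist". When the buffered solution is due, "the attending will prepare 1:10 dilution of sodium bicarbonate to local anesthesia", and the attending also loads the syringe. The operator and the child are blinded; the attending is not.

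Two further provisions matter. Section 5.1 numbers the children in order of entry: "each patient will be assigned number as they are added into the study. This number will be sequential". That number plays no part in allocation. Section 5.1 also sets up a locked spreadsheet, closed to the operator, that holds the number, visit dates, solution at each visit, technique, arch and side. Section 6 restricts the randomization sheet to the study physicians until the study ends.

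Section 5.5.1 plans paired t-tests, with repeated-measures ANOVA if covariates are identified. It names no visit, side or sequence term.

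**The concern.** Because the first-treated side is the chief-complaint or more carious side, visit order and side severity move together. The flip is all that keeps solution apart from both. It is made by someone who knows the child and will know the solution, and it is described among the steps for the procedure day. Section 5.1 asks for no prepared sequence, no concealed assignment, no witness and no record of the flip itself. It also does not ask that the first side be entered before the flip, and the caries fallback involves some judgement.

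A repeated or overridden flip would leave no trace. If the order departed from chance, any difference between first and second visit (or worse and better side) would enter the paired difference. A visit term would remove an average visit effect, but not fully a departure that depended on the child, such as one related to anxiety or to a painful tooth. Without any departure, the trial would still be unable to show a reader that its allocation was random.

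**Working it through.** **1. The plan's own figure.** Section 5.5.2 gives d = 0.50, 90% power, 44 evaluable and 55 enrolled with 20% attrition. Alpha and sidedness are not stated; I assume two-sided 5%. For a paired t-test with n = 44, the noncentrality is 0.50 × √44 = 3.317 on 43 df, and power is 0.900. Then 44 / 0.80 = 55. Both figures reproduce.

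**2. What the spreadsheet could reveal.** Let X be the number of children given buffered first, so X ~ Binomial(44, 0.5) if the flips are honest. A two-sided check at 5% rejects at a split of 29:15 or worse (actual size 4.9%). Its chance of rejecting under a true share q is:

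| True share, buffered first | Chance of detection |
|---|---|
| 60:40 | 26% |
| 65:35 | 52% |
| 70:30 | 78% |

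Steering by severity or anxiety that left the total near 50:50 would not show in this check at all.

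**3. What an honest coin allows.** P(27:17 or worse, either direction) = 2 × P(X ≥ 27) = 17.4%. A realised 27:17 split shifts the paired mean by (27 − 17)/44 = 0.23 of whatever visit/side effect exists. This averages to zero over repetitions, but the planned t-test does not adjust for it in the trial at hand.

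**4. Size of a departure, for illustration only.** Let p be the share given buffered first and v the visit/side effect, in SDs of the paired difference. Then bias = (2p − 1) × v. The documents give neither p nor v; the values below are assumed. With n = 44, two-sided 5%, noncentral t:

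| p | v | Bias (SD) | Type I error | Power at d = 0.50 if bias opposes buffering |
|---|---|---|---|---|
| 0.50 | any | 0 | 5.0% | 90% |
| 0.60 | 0.3 | 0.20 × 0.3 = 0.06 | 6.8% | 81% |
| 0.60 | 0.5 | 0.20 × 0.5 = 0.10 | 9.9% | 74% |
| 0.65 | 0.5 | 0.30 × 0.5 = 0.15 | 16.3% | 62% |

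These hold the SD of the paired difference fixed. If v is instead scaled to the SD without the visit effect, mixing the orders widens the SD to √(1 + 4p(1 − p)v²), and the last three type I errors become 6.6%, 9.0% and 14.2%. On that scale, power at v = 0.5 is already about 83% with honest flips, so not all of a shortfall from 90% would come from steering.

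**The case against.** The strongest reply is that the plan as written is sound on average: a fair coin cannot be predicted, and any systematic share other than one half requires the attending to disregard the protocol. That stands. The figures in step 4 size a hypothetical breach, not a consequence of the plan.

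Other parts of the reply also stand, and they rule out stronger readings that a reader might infer:

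- *That there is no audit trail, or that steering would always go unseen.* The locked sheet records solution, side and dates, and a 70:30 departure would be caught about 78% of the time. What is missing is an independent record of the flip, made when it happens.
- *That the attending alone holds the allocation.* Section 5.1 gives the attending access, and section 6 speaks of study physicians in the plural. Sole custody is not stated.
- *That enrolment could be selective.* Section 5.3 says: "Recruitment of study participants will be done by the treating pediatric dental resident or attending pediatric dentist at the time of exam". But consent and numbering come before the flip, and every child is due both solutions. The exposure is confined to order and side.
- *That the two sides may differ without limit.* Section 5.2.2 requires the same arch and comparable teeth, and section 5.1 requires both sides to be alike in infection status. These rules narrow side differences, though not visit-order effects.

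Blinding of the child, who rates pain, and of the operator, who scores FLACC, protects the assessments. It does not protect or document the allocation. The spreadsheet does not fill that gap either: it shows what was given, not whether chance chose it.

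**Conclusion.** The point holds as a weakness in concealment and verifiability, with a cheap remedy. It is not evidence of bias. Allocation depends on one flip by an unblinded person who knows the child, with no prior commitment and no independent record, and the available record is weak against moderate departures (26% detection at 60:40, 52% at 65:35). The detection figures assume 44 evaluable patients and a two-sided 5% check. The type I error range of 6.8% to 16.3% applies only if the flip is not honoured, and only under the assumed p and v. With honest flips the average bias is zero; what remains is a 17% chance of a 27:17 or worse split, in an analysis without a visit or side term. This should be changed, but the trial does not fail without it.

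**What to change.** In section 5.1, replace the flip with a solution-order list generated before enrolment by someone who neither treats nor supervises the children, in permuted blocks of varying size. Two layouts work:

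- one list keyed to the sequential study number already given at consent; or
- two separate lists, IANB and infiltration, each with its own counter.

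A single list keyed to the consent number cannot also be blocked within technique, because technique depends on the arch each child needs treated.

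Hold the list as numbered sealed envelopes or as a locked electronic file. Require the first-treated side and arch to be entered before the child's entry is opened, and log the date and time of opening. The attending can still open the entry and prepare the solution. State also whether a child who repeats the study procedures takes a new entry, since section 5.1 does not say how order is set for a second round.

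The cost is a short amendment, about an hour to generate the list, and preparing and storing the lists at the two clinics. No visits or patients are added, and the sample size stays at 44 evaluable and 55 enrolled. The change conceals each assignment until it is made and allows it to be checked afterwards. Because the attending still mixes the drug, it does not by itself rule out substitution at preparation.

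### As written, the buffered cartridge holds 10% more than the control and no matching step is described, so the operator's blind is vulnerable, chiefly for FLACC

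*Combined protocol and SAP*

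**What the plan says.** All of this is in section 5.1 of the combined protocol and SAP.

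- **Preparation.** The starting product is "A 1.7mL vial of commercially available 2% lidocaine hydrochloric acid with 1:100,000 epinephrine". The mixing step is tied to one visit: "During the appointment requiring the buffered local anesthesia solution, the attending will prepare 1:10 dilution of sodium bicarbonate to local anesthesia". The amount is given as "0.17mL of 8.4 percent sodium bicarbonate will be added into the local anesthesia cartridge to make the final preparation". A pH check follows: "The buffered solution will be tested using a pH tester". Handling of the control cartridge is not described.
- **Blinding.** The attending prepares the solution, carries the cartridge to the operatory and loads the syringe. The operator has no access to the allocation spreadsheet. The plan then states: "The operator and patient will remain blinded to the type of local anesthesia that is used".
- **Delivery.** A single resident treats the patients. The dose for an inferior alveolar nerve block (IANB) is 0.85 mL, also expressed as 50% of a 1.7 mL carpule. The infiltration dose is "0.425mL (25% volume of a 1.7mL carpule) of solution over 15 seconds".
- **Assessment.** "Patients will be observed during injection and assessed by the operator using the Faces, Legs, Arms, Crying Consolability (FLACC) scale". Who asks for the FACES rating, and who probes and asks about the pinch, is left in the passive voice. The operator enters all three outcomes: "This spreadsheet will be available to the operator in order to record the clinical outcomes related to each encounter".
- **Sequence.** The second visit always uses the other solution.

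**The concern.** Keeping the allocation sheet from the operator does not hide a physical difference between the two cartridges. On the text as written there is one, and the person holding the syringe is also the person who scores FLACC. Because each child's second solution is the alternate of the first, recognising the solution at one visit identifies it at the other.

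If the operator could tell the solutions apart, expectation could move the FLACC score in the hypothesised direction. The paired analysis does not remove this. Pairing cancels what is stable within a child, but a bias that follows the treatment goes straight into the paired difference. Pain on injection is the primary aim, and FLACC is one of its two measures. FACES and onset would be open to the same influence if the operator elicits them, which the wording does not settle.

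**Working it through.** **1. The plan's own sample size (section 5.5.2).** Inputs from the plan: d = 0.50, 90% power, 44 evaluable, 55 enrolled, 20% attrition. Assumed, because sections 5.5.1 and 5.5.2 do not state it: two-sided alpha of 0.05.
- Paired t-test, noncentral t with 43 df and noncentrality 0.50 × √44 = 3.317: power = 0.900.
- 44 / (1 − 0.20) = 55, and 20% of 55 = 11.

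The sample size reproduces. The point is about blinding and not about N.

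**2. Volume at the start.** Inputs from section 5.1: 1.7 mL cartridge, 0.17 mL added, no withdrawal described.
- Buffered: 1.7 + 0.17 = 1.87 mL. Control: 1.70 mL.
- Ratio: 1.87 / 1.70 = 1.10, that is +10%.

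**3. Volume left after the stated dose.**

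| Technique | Dose (mL) | Control left (mL) | Buffered left (mL) | Ratio |
|---|---|---|---|---|
| IANB | 0.85 | 1.70 − 0.85 = 0.85 | 1.87 − 0.85 = 1.02 | 1.20 |
| Infiltration | 0.425 | 1.70 − 0.425 = 1.275 | 1.87 − 0.425 = 1.445 | 1.13 |

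The absolute gap is 0.17 mL throughout.

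**4. Millilitres against percentages.** For the buffered cartridge the two expressions of the dose no longer agree.
- 0.85 / 1.87 = 45.5%, against the stated 50%. Half of 1.87 mL is 0.935 mL.
- 0.425 / 1.87 = 22.7%, against the stated 25%. A quarter of 1.87 mL is 0.4675 mL.

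**5. What an expectation shift would do (illustration only).** Let δ be the average shift favouring buffering, in SDs of the paired difference, with no true effect and n = 44. The noncentrality is δ√44 and the two-sided 0.05 critical value is 2.017 on 43 df. The table gives the upper-tail rejection probability, that is, a false result in favour of buffering.

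| δ | δ√44 | Probability |
|---|---|---|
| 0 | 0 | 2.5% |
| 0.1 | 0.663 | 9.5% |
| 0.2 | 1.327 | 25% |
| 0.3 | 1.990 | 49% |

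The documents supply no value for δ. For scale, the plan's target effect is 0.50. δ is an average over all children: if recognition worked in only half of them, a shift of 0.1 or 0.2 would become 0.05 or 0.10, giving 5.1% or 9.5%.

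**The case against.** The best defence is that the plan already separates the roles. The attending mixes, apparently outside the operatory, and loads the syringe, and the allocation sheet is locked. A swab, puncture or pH test done elsewhere is not seen by the operator. Doses are given in millilitres, no metering method is stated, and the percentages refer to a nominal 1.7 mL carpule. The operator sees one cartridge per visit, with at least a week between visits. The fill at injection is not certain either: a sample is pH-tested without a statement of its source or fate, and a site might in practice expel an equal volume first.

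Much of this stands, and it limits the point in five ways.

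- A reader might infer that the operator is unblinded. The documents show a route to unblinding, not that it happens.
- A reader might infer that the operator elicits all three outcomes. Only FLACC is explicitly the operator's. For FACES and onset the plan says who records them but not who asks.
- A reader might infer that the control cartridge receives no handling. Its handling is not described, which is weaker.
- A reader might treat the operator's access to first-visit scores as a separate breach. Without the allocation, an earlier score does not say which solution was given.
- The table of false-positive probabilities is not evidence that bias exists. Its shifts and its alpha are assumed.

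The objection does not remove the gap. No withdrawal, volume matching or blinding check is described. A dose expressed as a fraction of a carpule makes fill or stopper position a natural thing for the operator to look at. The only other clinician described at the visit is the attending, who knows the allocation, so reassigning assessments to that person would not help.

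**Conclusion.** The concern holds as a vulnerability of the stated double blind, chiefly for FLACC. As written, the buffered cartridge starts 10% fuller (1.87 against 1.70 mL). The difference in what remains is 20% after an IANB and 13% after an infiltration. FACES and onset are at risk only if the operator elicits them. The conclusion rests on taking the preparation text literally (no volume withdrawn or discarded) and on the operator being able to see the cartridge; the documents confirm neither.

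The consequence for inference cannot be sized from the documents. The illustrated rise from 2.5% to between about 9.5% and 49% depends entirely on assumed shifts of 0.1 to 0.3 SD and an assumed two-sided alpha of 0.05. The sample size is unaffected. The point merits action because the remedy is cheap and has to be in place before children are treated.

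**What to change.** 1. Out of the operator's sight, the attending, who already prepares and loads the cartridge, brings both cartridges to the same visible fill level before loading. One way is to discard the 0.17 mL surplus of the buffered mixture.
2. The attending wipes, punctures and holds the control cartridge in the same way and for the same time as the buffered one.
3. After each child's last visit, record the operator's guess of the solution, and report these guesses with the results.
4. State in section 5.1 who elicits FACES and who probes for onset.
5. Reconcile the dose passages, which give percentages of a 1.7 mL carpule, with the preparation passage, which yields 1.87 mL. The delivered volumes remain for the sponsor to define.

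An opaque sleeve, or any masking that could hide the cartridge, should not be used: section 5.1 requires aspiration in all cases, and covering the cartridge could interfere with that step.

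The cost is about a minute of the attending's time per visit, one extra data field and a short protocol amendment. No extra staff are needed.
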